1.0 Background

In the United States, every year approximately 1.7 million people sustain a traumatic brain injury (TBI) with the majority (80% or 1.4 millions) of these injuries falling into the category of concussion or mild TBI (mTBI).¹ Concussion is classified as a mild form of traumatic brain injury, while changes in neural function following concussions are far from benign. Concussed athletes frequently experience lingering neurological symptoms, including headache, irritability, blurred vision, and confusion.² In respect to these symptoms, researchers have utilized various metrics to study brain damage, including brain-derived blood biomarkers, sensory systems, and neuroimaging. However, due to exceedingly high intra-group variability in the concussed cohort, to date there is no gold standard metric to gauge severity of brain damage following head impacts.³

One possible explanation of the high variability is due to subconcussive head impact, defined as an impact to the head that does not cause any symptoms of concussion, regardless of magnitude of the impact. It, however, has the potential to cause insidious effects in the brain if sustained repetitively over time.⁴ An average athlete in contact sports experiences nearly a thousand subconcussive hits per season.⁵ While the vast majority of research has focused on a single impact that elicits concussion (e.g., disorientation, headache), many athletes are frequently exposed to subconcussive head impacts prior to the concussive blow.^{6, 7} Thus, it remains completely unknown whether neuronal damage and sensory deficit are caused by a single concussive blow, repetitive subconcussive impacts before the concussive blow, or both.

[figure not shown]
Ocular-motor System

Recently, the ocular-motor system has garnered significant scientific attention because of its sensitivity to various severities of brain injury.⁸ The ocular-motor system orchestrates accommodation and vergence, and their concomitant adjustment enables individuals to visualize an object at various distance, direction, and speed.⁹ Nearly 50% of the neural connections in the human brain, including cortical, cerebellar, and brainstem networks are involved in vision and eye movement functions. Since most head impacts cause the brain to bounce linearly and rotationally within the skull, almost 90% of concussed individuals exhibit some form of visual dysfunction.^{10, 11} For example, a notable decline in saccades –rapid changes in eye orientation– has been observed in concussed boxers, football, and rugby players.^{12, 13} Similarly, a near point of convergence (NPC), which is the closest point one can visualize an object before diplopia occurs, was impaired by 3-fold in concussed athletes and soldiers.^{14, 15} Neuroimaging confirmed that these ocular-motor impairments were in concert with altered neuronal activity after concussion.¹⁶

Previously, for the first time we have demonstrated that repetitive subconcussive head impacts could significantly impair NPC in soccer¹⁷ and football players.¹⁸ More intriguingly, the NPC has **predicted concussions** before they occurred. In our football study, we tracked changes in NPC in 25 players, and 3 of 25 players were diagnosed with a concussion (Fig 1: unpublished). There was a biphasic increase in NPC: 1) acute increase after 1st full-gear practice (Pads-ON1) compared with pre-practice, and 2) on the day of concussion, *3 players showed abnormally high NPC before the practice*. Due to absence of concussion signs and symptoms, the players participated in the practice. Following moderate intensity of impacts, the 3 players became unconscious for < 30

seconds and diagnosed with a concussion by team athletic trainers. Despite it is preliminary, the ocular-motor function has the potential for a paradigm shift in concussion diagnosis. However, it is imperative to first understand the acute effects of subconcussive head impacts on the ocular-motor system.

Fig 1. The near point of convergence (NPC) “predicted” concussion before it occurred.

Peripheral diagnostic tools for brain injury have an immense clinical implication, however those methods are insufficient to truly gauge neuronal dysfunction after head hits. Electroencephalography (EEG) has produced promising results in patient with

[figure not shown]

Fig 3. PINCH protein was detectable in mesial temporal epilepsy patients' blood. Robust plasma expression of PINCH was observed in both medically controlled (no seizure) and refractory (transient seizure) epilepsy patients, while no PINCH in healthy controls.

[figure not shown]

Fig 4. Post-season plasma PINCH was notably higher than pre-season baseline. 10 out of 16 players showed increase in plasma PINCH at post-season. * Player 5 and 13 did not play for the season due to surgery. Control: a subject with no history of head trauma. LB, linebacker; OL, offense lineman; WR, wide receiver; DL, defense lineman; DB, defensive back; RB, running back; TE, tight end.

concussion, with reduced mean frequency of alpha, reduced power in the alpha and beta frequency bands, hypercoherence between frontal regions, and decreased gamma frequency.²⁵⁻²⁹ In addition to EEG, transcranial magnetic stimulation (TMS) has garnered significant attention in scientific society recently, due to its non-invasive method to measure neuronal excitability. However, to date, there is virtually no literature demonstrating the effects of minor head impacts on neuronal activity using EEG nor TMS.

Soccer Heading Modality

Soccer heading is a common skill performed by soccer athletes during practice and games. An average collegiate soccer players perform about 500 headers during a single season and over 3000 during the course of a career^{30, 31} Research has demonstrated the need for increased awareness of potential brain injury associated with heading the soccer ball with some suggesting that the cumulative effect of soccer head impacts over a career may lead to outcomes similar to sustaining multiple concussions.³² Various studies have been conducted to examine the effect of an acute bout of soccer heading, including [name] previous laboratory at Temple University, with most authors reporting no significant effect of heading on the brain function measures of neuropsychological or balance performance (Table 1). We have tested collegiate soccer players post heading ball speed up to 50 mph with no significant alterations in common

clinical measures (e.g., balance error scoring system, signs and symptoms checklist). However, sensitive modalities like blood biomarker and ocular-motor testing begin to unravel subclinical perturbation caused by minor head hits if sustained repetitively.^{17, 18, 33}

Table 1. Research studies examining the effect of an acute bout of soccer heading

Author	Subject	Method	Outcome
Patukian et al. (2000)	100 college athletes	20 minutes of practice heading	NSD in neuropsychological performance
Broglio et al. (2004)	40 college Athletes	20 headers in 20 minutes	NSD in postural control
Magnus et al. (2004)	10 college Athletes	20 headers in 5 minutes	NSD in balance
Schmitt et al. (2004)	31 college athletes	18 headers in 40 minutes	NSD in postural control, Symptoms increased (headache, vertigo, fatigue)
Mussack et al. (2003)	amateur athletes 61 heading group 58 active controls	55 min of heading practice Exercise	Significant increase in S-100B in heading versus active control group
Stalnacke et al. (2004)	44 professional athletes	Soccer game	Significant increase in S-100B, +Correlation between S-100B and # of headers
Otto et al. (2005)	adult athletes	Boxing Marathon Running Soccer Heading (16 mph)	Significant increase in S-100B Significant increase in S-100B NSD in S-100B
Haran et al. (2013)	16 college athletes	Soccer Heading (25 mph)	Significant change in postural control using virtual environment 24h post.
Zetterberg et al. (2007)	23 amateur soccer players 10 Non-athletic subjects	20 headings	NSD in S100B between pre vs. post and heading vs. control group.
Dorminy et al. (2015)	16 college soccer players	5 headings at 30, 40, 50 mph	NSD in S100B nor concussion symptoms after soccer heading at any speed.
Kawata et al. (2016)	20 college soccer players	10 headings at 25mph	Significant decrease in ocular-motor function immediately after and 24h post heading.
Hwang et al. (2016)	20 college soccer players	10 headings at 25mph	Significant change in vestibular function at immediately after headings but NSD in 24h post-heading.
Kaminski et al. (2007)	71 college soccer players	Pre-post Season	NSD in balance, neurocognitive performance
Kontos et al. (2011)	63 youth soccer players	Heading exposure groups High vs. Moderate vs. Low	NSD in neurocognitive performance between groups

2.0 Rationale and Specific Aims

Aim 1. Determine acute effects of subconcussive head impact on plasma PINCH and tau expression using controlled soccer heading model.

Hypothesis: Repetitive subconcussive head impacts will significantly increase plasma PINCH level at 24h-post heading, but plasma PINCH at 0h- and 2h-post heading will remain undetectable, while there will be a significant increase in serum tau level at immediately post-heading (0h and 2h) but normalize to baseline level at 24h-post heading.

After a concussion, a neural network is often disturbed due to axonal injury, observed via neuroimaging.^{34, 35} Also, an acute increase in plasma tau has been observed in concussed athletes.³⁶ However, a half-life of tau protein in the blood is known to be short (~3h),³⁷ thus at 24h-post heading tau level is expected to normalize to the pre-heading baseline level. Recent preliminary findings showed that neural disturbance was notable in football players at post-season compared with pre-season baseline, as well as rugby players after a single rugby game compared with pre-game level.^{38, 39} Although subconcussive impacts do not cause concussion-related symptoms,¹⁸ neuronal axons are evidently experiencing pathological stress.⁴⁰ Repetitive subconcussive impacts likely to cause tau injury, and because PINCH continues to be over-expressed in the brain as long as tau is

damaged,^{21, 22} a fraction of PINCH will be detectable in the peripheral blood stream via glymphatic system or disrupted blood-brain barrier.³⁷

Aim 2. Determine acute effects of subconcussive head impact on dynamic gaze-target synchronization in a controlled soccer heading model.

Hypothesis: Repetitive subconcussive head impacts will significantly decrease saccadic velocity and smooth pursuit velocity gain, and increase gaze position error variability.

Soccer heading model is a safe and reliable method to study mild head impacts, with average impact magnitude of 14 g.^{17, 33} To track a moving object, the brain must predict the trajectory of the moving target and maintain focus by concomitant adjustment of eye movement. We will employ the Eye-Sync system, which objectively measures important parameters, including smooth pursuit velocity gain, saccadic peak velocity, gaze position error variability.

Aim 3. Inspect subconcussive effects on changes in neuronal activity during resting default mode.

Hypothesis: Subconcussive impacts will induce a significant suppression of theta, alpha and beta waves (powers) in the frontal and occipital brain region during resting default mode, compared with baseline levels.

Since subconcussive impacts induce diffuse force to the brain, rather than a focal injury like contusion,⁴ likely neuronal network is disrupted. Neuronal activity –delta, theta, alpha, beta powers– in the whole brain will be measured using electroencephalography (EEG) while resting.

Aim 4. Determine whether subconcussive head impacts induce physiological effects in primary motor cortex.

Hypothesis: Subconcussive impacts will significantly reduce primary motor cortex excitability compared with baseline levels.

To better characterize neuronal physiology after subconcussive impacts, we will employ transcranial magnetic stimulation (TMS) to detect subclinical, physiological change in the primary motor cortex (M1). Consistent with established protocol,⁴¹ we will target the M1 representation of a finger muscle at baseline and each post-heading time point to compute the input/output (I/O) curve, which reflects M1 excitability.

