8.0 Statistical Considerations

Power analysis

According to our previous studies [Kawata et al. (2016)¹⁷ and Hwang et al. (2016)³³] and preliminary findings (Fig 4), the effect size is estimated to be 0.55 and the standard deviation is approximately 0.6. To achieve a power of 0.80 with $p < 0.05$ as significance level, 18.68 subjects per group are suggested for the studies (Formula on the right). Although we did not have any drop-outs in aforementioned previous studies, the study would need 20 subjects per group to be able to interpret the data with any degree of confidence regarding the effects of subconcussive head impacts on outcome measures. Since we are recruiting 10 subjects per group for TMS and EEG for pilot studies, subsequent power analyses will be performed following data collection to determine whether we will need additional sample size or not.

$$n = \frac{Z_{\alpha} \quad Z_{1-\beta} \quad SD}{\text{Effect Size}^2} = \frac{2(1.96 + 0.8416)^2 (0.6)^2}{(0.55)^2}$$

Data analysis

Data analysis will be conducted by [name], associate professor of biostatistics and director of biostatistics counseling center. To maintain the purity of statistical analyses, [name] will be blinded to group assignments by simply given the data set indicating Group (A, B, C). However, for our statistical model of longitudinal assessment, time points (pre, 0h-post, 2h-post, 24h-post) will be revealed to [name].

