Our primary interest is to identify the changes in biomarker expression, ocular-motor, and neural function after subconcussive head impacts in the heading group; hence, each parameter at post-heading time points (0h, 2h, and 24h) will be compared with pre-heading baseline. Each time point of the control groups (kicking and standing) will aid to interpret whether or not changes in the heading group are due to subconcussive impact, exercise, bodily hit, or simply a daily variation. To this end, a series of mixed effects regression models (MRM) with random intercept will be used for all aims.⁴⁸ The first MRM will focus on the within-group pattern of changes in biomarker expressions (PINCH and Tau), ocular-motor performance (smooth pursuit velocity gain, phase error, and gaze position error), neural activity (delta, theta, alpha, and beta powers), and motor cortex excitability (I/O curve) in 3 groups across the duration of the study – 4 time points. Next MRM will focus on between-group analyses on the variables (heading, kicking, standing) against changes in the biomarker levels, ocular-motor function, and neural function. Predictor variables include time, group, and time by group interaction. All analyses will be conducted with SAS and significance will be set at $p < 0.05$.

Study Endpoint

Throughout the study, we set the study endpoint based on subjects' well-being measured via symptom checklist or verbal claim to researchers. Because the mild nature of head impact, we expect to observe a subtle change in our sensitive outcome variables after soccer headers. To date, there is virtually no scientific evidence available to set study endpoints using ocular-motor, blood biomarker, and neuronal activity, we will guide the study based on symptoms, meaning that if a subject experiences any concussion-related symptoms following blood draw, soccer heading, ocular-motor testing, EEG, and TMS, his or her participation will be terminated.

Symptom

When a subject experiences any symptoms related to concussion (headache, nausea, blurred vision, disorientation, fogginess, sensitivity to light and noise, etc.), his/her participation will be terminated. However, there has been no participant thus far reported concussion-related symptoms due to soccer heading, blood draw, nor ocular-motor performance.

Blood Biomarker

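### Aim 1 predicts no change for tau at 24h and for PINCH at 0h and 2h, but the protocol states only tests of difference at p < 0.05, and a non-significant result cannot support those predictions

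*Protocol*

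**What the plan says.** The hypothesis under Aim 1 (Protocol, section 2.0) makes six marker-by-time predictions for the heading group. Three are increases: tau at 0h, tau at 2h and PINCH at 24h. Three predict no change. For tau the full course is a "significant increase in serum tau level at immediately post-heading (0h and 2h) but normalize to baseline level at 24h-post heading". For PINCH, "plasma PINCH at 0h- and 2h-post heading will remain undetectable". The rationale bases the 24h tau prediction on a half-life in blood of about 3h: "thus at 24h-post heading tau level is expected to normalize to the pre-heading baseline level".

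Section 8.0 (Data analysis) gives the primary interest as identifying changes after heading, so that "each parameter at post-heading time points (0h, 2h, and 24h) will be compared with pre-heading baseline". It adds a second mixed model: "Next MRM will focus on between-group analyses on the variables (heading, kicking, standing) against changes in the biomarker levels". On the model terms it says "Predictor variables include time, group, and time by group interaction". One significance level, 0.05, applies to all analyses. The Power analysis in the same section sizes the study to detect a difference.

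The protocol gives no margin or interval criterion for deciding that tau has normalised. It gives no detection limit for PINCH and no analysis of detectable against undetectable samples.

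**The concern.** The hypothesis and the stated analyses do not fit each other. A difference test can support the three predicted increases. The prediction that tau is back at baseline at 24h can only be left standing by failing to reject, and a small group often fails to reject when part of the rise remains.

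The PINCH predictions raise a different problem. Undetectable describes each sample against an assay limit. A regression on mean levels does not measure that, whatever its p-value, and it suits poorly a marker expected to be mostly below detection at baseline, 0h and 2h.

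The time course is the reason for sampling at 0h, 2h and 24h. The reading that tau rises early and clears while PINCH appears late is the substance of Aim 1, and its no-change half would rest on absence of significance. Table 1 in section 1.0 already summarises an earlier study of the same heading model as a change immediately after heading and no significant difference at 24h, so a reader could easily take such a result as recovery.

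**Working it through.** **Inputs from section 8.0, Power analysis.** Effect 0.55 (entered as a raw difference), SD 0.6, two-sided 5% level, power 0.80, 20 subjects per group.

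**Assumed, because the protocol does not give them.** The within-subject correlation ρ between two time points, taken from 0 to 0.9. The change still present at 24h: half the design effect (0.55/2 = 0.275) or a quarter (0.55/4 = 0.1375).

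**Step 1: the plan's own figure.** The numerator is "2(1.96 + 0.8416)^2 (0.6)^2" = 2 × 7.849 × 0.36 = 5.651. Dividing by 0.55² = 0.3025 gives 18.68, as stated. With 20 per group, power for a difference of 0.55 is 80.6% (t test). This gives no assurance about a conclusion of no change.

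**Step 2: how often the 24h test misses a residual rise.** For a paired comparison in the heading group, SD of change = 0.6 × √(2(1 − ρ)) and SE = SD/√20. The critical value is t(19) = 2.093. The probability of p ≥ 0.05 comes from the noncentral t distribution with noncentrality residual/SE. At ρ = 0.5: SD = 0.600, SE = 0.134, noncentrality = 0.275/0.134 = 2.05, probability 51%.

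| ρ | SD of change | 95% CI half-width | p ≥ 0.05 if 0.275 remains | p ≥ 0.05 if 0.1375 remains |
|---|---|---|---|---|
| 0 | 0.849 | 0.40 | 72% | 89% |
| 0.3 | 0.710 | 0.33 | 62% | 87% |
| 0.5 | 0.600 | 0.28 | 51% | 84% |
| 0.7 | 0.465 | 0.22 | 29% | 76% |
| 0.9 | 0.268 | 0.13 | 1% | 42% |

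At ρ of 0.5 or below, the half-width is at least 0.28, so an interval centred exactly on zero would not exclude a residual of 0.275.

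The paired t test stands in for the planned mixed model. Pooling the residual variance over four times and three groups of 20 gives 3 × 19 × 3 = 171 degrees of freedom and a critical value of 1.974. The entry at ρ = 0.5 and residual 0.275 then falls from 51% to 47%, so the picture does not change.

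**Step 3: what an equivalence criterion would cost.** The test is two one-sided tests at 5%, true change zero, 20 subjects. With a margin of 0.275, power is 2%, 10%, 27%, 64% and 99% for ρ = 0, 0.3, 0.5, 0.7 and 0.9. With a margin of 0.55 it is 75%, 91%, 98%, and above 99% for the last two. The protocol states no margin, so these are illustrations.

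**Step 4: PINCH.** If 0 of 20 samples are detectable, the upper limit of the exact two-sided 95% interval is 1 − 0.025^(1/20) = 16.8%.

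**The case against.** **Nothing in the protocol says that p > 0.05 will be read as recovery.** This is correct. A reader might infer that the sponsor has committed to that reading, but no such rule is written: the primary interest is detecting change, and the 24h tau statement is partly a biological expectation. What stands is that it is also part of the formal hypothesis, and no stated analysis can support it.

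**Comparison with baseline is not the only test.** Also correct. Section 8.0 has a between-group model with a time-by-group interaction, and the four-level time factor already allows a 2h-to-24h contrast. The stated comparisons are still tests of difference, so the conclusion is unchanged.

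**A half-life of about 3h makes a large residual implausible.** From 0h to 24h is 24/3 = 8 half-lives, leaving 2⁻⁸ = 0.4% of the rise. That holds only if release has stopped. The same rationale says PINCH stays over-expressed for as long as tau is damaged, and predicts PINCH at 24h. Continued release is therefore not excluded by the protocol's own mechanism.

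**The inputs are not about tau.** They come from two earlier heading studies, on near point of convergence and vestibular function, and from preliminary PINCH data. The correlation is assumed and moves the result from 72% to 1%. The percentages therefore show how the rule behaves and do not forecast this trial.

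**PINCH is not an equivalence problem.** Agreed: it is settled by counting samples. The protocol itself summarises its preliminary PINCH data as numbers of players, yet the planned model treats PINCH as a level. The gap there is a mismatch between hypothesis and analysis.

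**Margins and contrasts belong in a statistical analysis plan.** Such a plan may exist and supply them, and their absence alone would be no finding. The point is that the protocol fixes both the hypothesis and the type of test, and the two do not match.

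**Conclusion.** The point holds as a mismatch between hypothesis and analysis. Three of the six Aim 1 predictions are of no change, and every comparison stated in section 8.0 is a test of difference. The inferential objection applies in full to tau at 24h; for the two PINCH predictions the fault is that a mean-level model does not answer a question about detectability.

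For tau, if half the design effect persisted, the 24h test would be non-significant in 51% of trials at a correlation of 0.5, with a range of 72% to 1% for correlations of 0 to 0.9. This rests on borrowed inputs (0.55 and 0.6), 20 subjects in the heading group and an assumed correlation.

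A reader might go further and conclude that the study is undersized or that Aim 1 cannot be tested. The documents do not support that: the stated sample size reproduces, and the three predicted increases can be tested as planned. This should be corrected, but it does not undermine the trial.

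**What to change.** Add to section 8.0, Data analysis, for Aim 1:

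- **Tau.** Estimate the 2h-to-24h contrast from the same mixed model. Report the 95% CI of 24h minus baseline in the heading group, and of that change against the kicking and standing groups. State that normalisation will not be concluded from p > 0.05 alone. Then either judge it against a fixed margin set before unblinding, or label the 24h prediction descriptive. The margin should not be a fraction of the rise observed in the trial: that depends on the data, ignores the uncertainty in the rise and has no meaning if tau does not rise.
- **PINCH.** State the assay detection limit. Report the number of subjects above it at each time point, by group, with exact 95% CIs. Do not infer undetectability from a non-significant mean change.

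The cost is a few lines of text and no new samples. The downside is real: normalisation at 24h becomes harder to claim. With 20 subjects and a margin as tight as 0.275, a finding of not shown to have normalised is likely even if tau has fully returned to baseline, unless the within-subject correlation is high. If the sponsor does not want that outcome, labelling the prediction descriptive is the simpler choice.
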